# **Derived Variables and Statistical Analysis:**

The total CY-BOCS-II score is computed as the sum of the consensus rating on items 1-10, range = 0 (no symptoms) to 50 (extreme symptoms), whereas the obsession and compulsion subtotals are the sums of items 1-5 and 6-10, respectively. Higher scores indicating more severe compulsions and obsessions. Missing values will not be imputed.

The total score will be summarized by treatment group at the Baseline and Weeks 4, 8, 12, 13, 14, 15, 16, 20, and 24 visits and all questionnaire data will be displayed in a listing.

#### 12.7.6. Patient Health Questionnaire-9 (PHQ-9)

The PHQ-9 is a validated, 9-question instrument to assess the degree of depression present in adults (18 years of age and older). The PHQ-9 incorporates DSM-4 depression diagnostic criteria with other leading major depressive symptoms into a brief, self-report questionnaire. The questionnaire rates the frequency of the symptoms which factors into the scoring severity index. Question 9 on the PHQ-9 screens for the presence and duration of suicide ideation. The clinician will perform suicide risk assessment in subjects who respond positively to question 9. A follow-up, non-scored question screens and assigns weight to the degree to which depressive problems have affected the subject's level of function.

## **Derived Variables and Statistical Analysis:**

As a severity measure, the PHQ-9 scores 9 items from 0 (not at all) to 3 (nearly every day) with total score range from 0 to 27.

The total score (sum of all items without imputing missing values) will be summarized by treatment group at the Baseline and Weeks 4, 8, 12, 13, 14, 15, 16, 18, 20, 22 and 24 visits and all questionnaire data will be displayed in a listing.

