| | | | Open-Label | Stabilizatio | on Period | | | | | | | | | | | | |
|---|--|------------------------------|--|--|---------------------------------------|--|---------------------------------------|---------------------------------------|---|---|--|---|--|---|--------------------------------------|--|---|
| | Screening Period ^a | Titrati | on Phase | W | tenance Pleeks 4 to 1 y 29 up to 8 | 2 | | | Double-Bli | Week | mized Withd as 12 to 24 85 to 169) | lrawal Perio | od | | | fety Follo Days 170 | |
| Visit/TC Study Day | Screening VISIT 1 Day -28 to -1 | Baseline VISIT 2 Day 1 | W 2 f Day 15 Telephone call only (±3d) | W4 / VISIT 3/ Day 29 (±3d) | W8 / VISIT 4 / Day 57 (±3d) | W 12 VISIT 5 Day 85 (±3d) | W13 / VISIT 6 / Day 92 (±3d) | W14 / VISIT 7 / Day 99 (±3d) | W15 / VISIT 8 / Day 106 (±3d) | W16 / VISIT 9 / Day 113 (±3d) | W18 / VISIT 10 / Day 127 (±3d) | W20 / VISIT 11 / Day 141 (±3d) | W22 / VISIT 12/ Day 155 (±3d) | W 24 VISIT 13 Day 169 or Relapse or ET (±3d) | 7 Day F/U VISIT 14 (±3d) | 14 Day F/U VISIT 15 (±3d) | 30 Day F/U ^f Telephone call only (±3d) |
| Extrapyramidal Symptom Rating Scale | | X | | X | X | X | X | X | Х | X | X | X | X | X | | | |
| Swanson, Nolan, and Pelham Questionnaire-IV- 26 ^h | | X | | X | X | X | X | X | X | X | | X | | X | | | |
| Children's Yale- Brown Obsessive Compulsive Scale- II ^h | | X | | X | X | X | x | Х | X | X | | X | | X | | | |
| Patient Health Questionnaire-9g | X | X | | X | Х | X | Х | X | X | X | | X | | X | | | |
| Hamilton Rating Scale for Anxiety ^g | | X | | X | X | X | X | X | X | X | | X | | X | | | |
| Conners' Adult ADHD Rating Scale ^g | | X | | X | X | X | X | X | X | X | | X | | X | | | |
| Yale-Brown Obsessive Compulsive Scale- II ^g | | X | | X | X | X | X | X | X | X | | X | | X | | | |
| PK Blood Draws ^{d,e} | | | | X | X | X | | | | | | | | | | | |
| Adverse Events | X | X | X | X | X | X | X | X | X | X | X | X | X | X | X | X | X |
| Concomitant Medications | X | X | | X | X | X | X | X | X | X | X | X | X | X | X | X | |

Confidential

Page 41 of 96

Protocol EBS-101-TD-301 Version 9.0, 05 March 2024

| | | | Open-Label | Stabilizatio | on Period | | | | | | | | | | | | |
|--|--|------------------------------|--|--|---|--|---------------------------------------|---|---|---|---|---|--|---|--------------------------------------|--|---|

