# 8. General Aspects for Statistical Analysis

#### 8.1. General Methods

Study EBS-101-TD-301 is a multicenter global study. Investigative sites in the US are considered conducted under IND 109746 and non-US investigative sites are considered not conducted under IND 109746. Tables, Listings, and Figures will contain combined data from IND and non-IND investigative sites.

All analyses and outputs will be produced using SAS® version 9.4 or later. Unless otherwise specified, efficacy and safety summaries will be presented for each treatment. Continuous variables will be summarized using the number of observations (n), mean, standard deviation (SD), median, minimum, and maximum. Categorical variables will be summarized using number of observations (n), frequency, and percentages of subjects. Time-to-event variables will be summarized using Kaplan-Meier estimates of the 25th percentile, median and 75th percentile.

All relevant subject data will be included in listings. All subjects entered into the database will be included in subject data listings. All by-visit summaries will use the nominal visit. Unscheduled visits will not be summarized but will be included in the listings.

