### 8.2. Key Definitions and Derivations

Treatment emergent adverse events (TEAEs) are defined as any adverse events that start or increase in intensity on or after the first dose of treatment on Day 1.

Timing-specific adverse events are defined as any adverse events that occur or increase in intensity during any specifically defined study milestones: open-label stabilization period (OLAE), double-blind R/WD phase (RWDAE), taper down (TDAE) and off study drug (ODAE).

Prior medications are defined as medications entered in the eCRF that either start, or end before the first dose of study medication. Concomitant medications are defined as medication on the eCRF that are taken on or after or are ongoing at the start date of dosing.

Duration of exposure (days) to study drug is defined as (Date of Last Dose – Date of First Dose) +1. If the date of last dose is unknown, then the date of last clinical visit will be used to impute the date of last dose.

Baseline is defined as the last measurement taken before the first dose of ecopipam in the open-label stabilization period.

Change from baseline will be calculated for the post-baseline assessments as post-baseline value – baseline value. Similarly, change from randomization will be calculated for the post-randomization assessments as post-randomization value – randomization value.

Demographics and baseline characteristics will be derived as follows:

Age at Study Day 1 = (Study day 1 visit date - date of birth + 1) / 365.25 and truncated to complete years.

Height (in cm) = height (in inches) \* 2.54

This document is confidential.

SAP text Version: SAP text 3.0 6-Dec-2023

Controlled Document ID: 3903A.02, Effective Date 31-Aug-2020

Weight (in kg) = weight (in lbs) \* 0.4536

BMI (kg/m2) = Weight(kg)/[Height(m)2]

To calculate weight, height and BMI z-scores for children and adolescents, Centers for Disease Control and Prevention (CDC) growth charts will be used (see section 13)

For adults, weight, height and BMI z-scores will be calculated as follows:

(Weight, Height and BMI) z-scores = (Weight, Height and BMI) - mean (Weight, Height and BMI) of all subjects at the baseline visit/ Standard deviation of (Weight, Height and BMI) of all subjects at the baseline visit.

Treatment compliance, as a percentage, will be derived on the eCRF as follows:

Treatment compliance (%) = Actual Tablets Used\*100/Expected Tablets Used

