#### 8.4. Visit Windows

The following visit windows will be used in the summarization or analysis of data. If the subject's last non-missing data point falls within the window, even if additional data points fall within the window, then that last data point will be used. Else, if more than 1 data point falls within a window then the data point closest to the target day will be used. If there are 2 data points equidistant to the target day, one high and one low, then the high data point will be used. Visit windowing will not be applicable to follow-up visits. If a subject terminates the study early, all assessments collected at the Early Termination visit will be assigned to the next scheduled visit (per Schedule of Assessments for the parameter) where the assessment would have been collected.

If Baseline is Day 1, then:

Day 15 (target day = 15) 2 - 21 and no randomization

Week 4 (target day = 29) 22 - 42 and no randomization

Week 8 (target day = 57) 43 - 70 and no randomization

Week 12 (target day = 85) 71 and above with no randomization

Week 13 (target day = 92) 78 - 95 and randomized

Week 14 (target day = 99) 96 - 102 and randomized

Week 15 (target day = 106) 103 - 109 and randomized

Week 16 (target day = 113) 110 - 119 and randomized

Week 18 (target day = 127) 120 - 133 and randomized

Week 20 (target day = 141) 134 - 147 and randomized

Week 22 (target day = 155) 148 - 161 and randomized

Week 24 (target day = 169) 162 and above (randomized and not a follow-up visit)

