#### 12.2. Laboratory Evaluations

Blood samples for hematology, chemistry, prolactin and urine samples for urinalysis are to be collected at screening, Baseline, Weeks 12 and 18, Completion [Week 24] or Relapse/Early Termination and 7 day and 14 day Follow Up visits. All results will be provided using International System of Units (SI). HbA1c will be measured at the baseline, week 12 and week 24 completion or early termination visits.

Descriptive statistics for hematology, chemistry, prolactin and HbA1c will be provided for each test parameter and for change from baseline treatment by visit and for each treatment group. Shift tables (i.e., low-normal-high at Baseline versus low-normal-high at each post-baseline visit in a 3-by-3 contingency table) will be provided for hematology, chemistry, prolactin, HbA1c and urine to assess changes from Baseline in laboratory values by visit for each treatment group. Shift (0.5% change) from baseline will be summarized for HbA1c by visit for each treatment group.

Separate listings will be provided for all laboratory evaluations (hematology, chemistry, prolactin, HbA1c and urinalysis.

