### Derived Variables and Statistical Analysis:

The 7-severity item is used to determine severity of symptoms and the PARS total score. Each severity item is coded from zero (none) to 5 (most extreme). Not applicable is coded to 8 and does not know is coded to 9. The total score for the PARS is total of the 7 severity items without imputing missing values. The total score ranges from 0 to 35. Codes "8" and "9" are not included in the summation.

The total score will be summarized by treatment group at the Baseline and Weeks 4, 8, 12, 13, 14, 15, 16, 20, and 24 visits and all questionnaire data will be displayed in a listing.

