## Derived Variables and Statistical Analysis:

Total scores range from 0 to 56 with higher scores indicating more severity.

The total score (sum of all items without imputing missing values) will be summarized by treatment group at the Baseline and Weeks 4, 8, 12, 13, 14, 15, 16, 20 and 24 visits and all questionnaire data will be displayed in a listing.

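### SAP 12.7 assigns no within-subject output to PARS, CY-BOCS-II, PHQ-9, HAM-A and Y-BOCS-II, and adult PHQ-9 has no counterpart to the CDRS-R shift table (optional, cheap improvement)

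*SAP*

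**What the plan says.** SAP 12.7 handles the five scales almost identically.

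- PHQ-9 (12.7.6): "The total score (sum of all items without imputing missing values) will be summarized by treatment group at the Baseline and Weeks 4" and further visits, with a listing.
- PARS (12.7.2) and CY-BOCS-II (12.7.5): "The total score will be summarized by treatment group at the Baseline and Weeks 4, 8, 12, 13, 14, 15, 16, 20, and 24 visits", with a listing.
- HAM-A (12.7.7) and Y-BOCS-II (12.7.9): the total score "will be summarized by treatment group at the Baseline and Weeks 4, 8, 12, 13, 14, 15, 16, 20 and 24 visits", with a listing.

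Under SAP 8.1 a continuous variable is summarized by n, mean, SD, median, minimum and maximum. SAP 8.2 defines change from baseline in general terms and adds that "change from randomization will be calculated for the post-randomization assessments". Section 12.7 assigns neither change score to a table for these scales.

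Other safety data are treated differently. For laboratory tests, "Descriptive statistics for hematology, chemistry, prolactin and HbA1c will be provided for each test parameter and for change from baseline", together with shift tables. Vital signs and ECG also have named change, shift or outlier outputs. CDRS-R (12.7.1) has a shift table from Baseline, cut at 40, by visit and arm.

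For PHQ-9, Protocol 8.2 (criterion 14) excludes adults scoring 10 or more at Screening or Baseline. Protocol 7.5 treats CDRS-R and PHQ-9 alike as possible grounds for discontinuation. Protocol 13.4.2 asks only for a descriptive summary of these scales.

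**The concern.** Safety and tolerability are a secondary objective, and Protocol 5.3.3 gives these scales the job of detecting worsening of other psychiatric symptoms. That is a question about each subject against his or her own starting value. A by-visit total answers a different one: the distribution of scores among whoever is still assessed at that visit.

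This matters more in a randomized withdrawal design. Relapsers and early leavers drop out of later rows at different rates in the two arms, and a subject who worsens psychiatrically may be one who leaves. Adult depression, anxiety and obsessive-compulsive symptoms all appear on the SAP 16.5 list of events associated with dopamine antagonists. The difference between the two depression scales is the clearest gap: children get a shift table and adults do not, with no reason given.

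At stake is how readable the descriptive safety output is. Relapse, power and alpha are not involved.

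**Working it through.** No figure in the plan belongs to this point. The sponsor's relapse inputs used below are consistent with its event target: 49 × 0.65 + 49 × 0.34 = 48.5, against 49 planned events.

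**1. Can the planned statistics hide worsening?** Take ten adults (invented scores) with Week 12 PHQ-9 of 1, 9, 2, 8, 3, 7, 4, 6, 5, 5 and later scores, in the same order, of 9, 1, 8, 2, 7, 3, 6, 4, 5, 5. Both visits give mean 5.0, SD 2.58, median 5, minimum 1 and maximum 9. Yet four of ten worsened, by 8, 6, 4 and 2 points. None reached 10, so a threshold count alone would also miss them; a within-subject change would not.

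**2. How unequal do the rows become?** Inputs are 49 per arm and 12-week relapse of 65% (placebo) and 34% (ecopipam), from Protocol 13.5. Assumptions: constant hazard, no other dropout, and PARS done at the relapse visit. With t in weeks after randomization, S(t) = (1 − R)^(t/12).

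- Relapse-free after Week 16: placebo 49 × 0.35^(4/12) = 34.5; ecopipam 49 × 0.66^(4/12) = 42.7.
- Relapse-free after Week 20: placebo 49 × 0.35^(8/12) = 24.3; ecopipam 49 × 0.66^(8/12) = 37.1.

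In the R/WD period PARS is scheduled at Weeks 13, 14, 15, 16, 20 and 24. Two SAP rules compete for relapse scores. SAP 8.4 says "all assessments collected at the Early Termination visit will be assigned to the next scheduled visit" at which the scale would have been collected. SAP 8.1 says "All by-visit summaries will use the nominal visit", and the schedule in Protocol Table 3 has one combined final column, "Day 169 or Relapse or ET".

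- Week 20 row. Under 8.4 a Week 18 relapse score moves to Week 20, so the row holds those relapse-free after Week 16: about 35 and 43. Under the nominal-visit reading, Week 18 and Week 20 relapses sit in the combined column, leaving about 24 and 37.
- Week 24 row. Under 8.4 a Week 22 relapse score moves to Week 24, and a Week 24 relapser is assessed at Week 24. The row therefore holds those relapse-free after Week 20: about 24 placebo and 37 ecopipam. Under the nominal-visit reading it holds up to 49 and 49.

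**3. Assessments per subject.** Expected R/WD PARS assessments, counting the relapse visit, are 1 + S(1) + S(2) + S(3) + S(4) + S(8).

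- Placebo: 1 + 0.916 + 0.839 + 0.769 + 0.705 + 0.497 = 4.7.
- Ecopipam: 1 + 0.966 + 0.933 + 0.901 + 0.871 + 0.758 = 5.4.

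**4. Sensitivity of a visit mean.** Anxiety was reported as an AE by 5.3% on ecopipam in the phase 2b study (Protocol 5.2.2). Applied to 196 children and adolescents, 0.053 × 196 = 10.4. If each rose 5 to 10 PARS points at one visit (assumed; scale 0 to 35), the mean would move 0.053 × 5 = 0.27 to 0.053 × 10 = 0.53 points.

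**5. Adults.** About 40 are expected. The documents give a 50% response rate only for children and adolescents. If it held for adults, 40 × 0.5 / 2 = 10 per arm; at 30% and 70% response, 6 and 14.

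**The case against.** The plan does what the protocol asked, since Protocol 13.4.2 requires no more than description. The psychiatric events of most interest will also appear elsewhere: AE tables by term, severity and time, AEs leading to termination, discontinuation reasons by period, C-SSRS counts and full listings. The ten anxiety cases in step 4 are themselves AEs and would already be counted. Because eligible adults enter below 10 on PHQ-9, a visit maximum of 10 or more already shows that someone crossed. With about ten adults per arm, the listing can be read directly. Worst change has its own flaw: it grows with the number of assessments, and ecopipam subjects have more of them.

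Most of this stands and sets the priority low. It does not remove the point. An AE report and a scale score are different measurements, a maximum does not say how many subjects crossed, and a listing is not a summary.

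Some stronger inferences are tempting, and the documents do not support them:

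- That the AESI tables omit depression, anxiety and obsessive-compulsive events. SAP 12.1 names three groups as included and refers to 16.5, which lists all of these. Coverage is unclear, not absent.
- That change will certainly not be tabulated. SAP 8.2 defines it generally and the shells were not seen. Mean-change columns may exist, although they would still not count subjects.
- That the Week 24 row under SAP 8.4 falls to those relapse-free at the end (49 × 0.35 = 17 and 49 × 0.66 = 32). That ignores relapses at Weeks 22 and 24, whose scores land in that row.
- That a psychiatric signal is being concealed. In the extension study, anxiety and depression led the AEs causing termination with two subjects each (1.7%). Protocol 5.2.2 reports no clinically significant difference from placebo on the anxiety and depression scales in phase 2b.

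**Conclusion.** The point holds as a low-priority improvement and not as an error. For five psychiatric scales, SAP 12.7 names total score by arm and visit plus a listing, and assigns no within-subject change, shift or threshold output. The case is strongest for PHQ-9, where the protocol already supplies a cut-off and the paediatric counterpart already has a shift table.

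The size is modest. On the stated relapse rates and an assumed constant hazard, the Week 20 PARS row compares 24 to 35 placebo with 37 to 43 ecopipam subjects. The Week 24 row compares about 24 with 37, or up to 49 with 49, depending on which visit rule is applied. None of these rows gives within-subject worsening. Adult counts will be small under any plausible response rate.

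The other scales are outside the point. ESRS scores of 1 or more are adjudicated. SNAP-IV and CAARS show the same pattern on subscales, but ADHD is not on the 16.5 list.

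**What to change.** Main change, SAP 12.7.6: add n (%) of adults with any post-baseline PHQ-9 score of 10 or more in the open-label period, and any post-randomization score of 10 or more in the R/WD period by arm, counting the Relapse/ET assessment. Label 10 as the protocol's entry cut-off and not as a threshold for meaningful worsening.

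Secondary change: for PARS, CY-BOCS-II, PHQ-9, HAM-A and Y-BOCS-II, summarize each subject's worst change from Baseline (open-label) and from Week 12 (R/WD, by arm), using the SAP 8.2 definitions and including Relapse/ET. Print the number of assessments per arm beside it, because a worst value rises with the number of visits (about 5.4 ecopipam against 4.7 placebo for PARS). This gives the distribution of worst change. It is not a count of worsened subjects, since the documents supply no worsening threshold for these scales.

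Clerical: remove Weeks 18 and 22 from the PHQ-9 visit list in 12.7.6, since the schedule does not collect PHQ-9 then.

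The cost is SAP wording, ideally settled before unblinding, and a few descriptive tables from data already collected. No visit, procedure or test is added.

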#### 12.7.7. Hamilton Rating Scale for Anxiety (HAM-A)

The HAM-A is a clinician rated instrument for assessing the severity of anxiety symptoms in adults. The HAM-A consists of 14 items, each defined by a series of symptoms, and measures both psychic anxiety (mental agitation and psychological distress) and somatic anxiety (physical complaints related to anxiety). Each item is scored on a scale of 0 (not present) to 4 (severe).

## Derived Variables and Statistical Analysis:

Total scores range from 0 to 56 with higher scores indicating more severity.

The total score (sum of all items without imputing missing values) will be summarized by treatment group at the Baseline and Weeks 4, 8, 12, 13, 14, 15, 16, 20 and 24 visits and all questionnaire data will be displayed in a listing.

## 12.7.8. Conners' Adult ADHD Rating Scale- Self Report, Short Version (CAARS-S:S)

The CAARS is a 26-items self-report questionnaire assessing the severity of ADHD symptoms in adults. Subjects are asked to rate themselves on a range of symptoms and behaviors associated with ADHD in adults. Each item is scored on 4-point scale (0 = Not at all, never; 1 = Just a little, once in a while; 2 = Pretty much, often; and 3 = Very much, very frequently).

## Derived Variables and Statistical Analysis:

Subscale raw scores are calculated by summing the scores on the items in the subset. The subscales (Inattention/Memory Problems, Hyperactivity/Restlessness, Impulsivity/Emotional Lability, Problems with Self-Concept, ADHD Index) will be summarized by treatment group at the Baseline and Weeks 4, 8, 12, 13, 14, 15, 16, 20, and 24 visits and all questionnaire data will be displayed in a listing.

# 12.7.9. Yale-Brown Obsessive Compulsive Scale-II (Y-BOCS-II)

The Y-BOCS-II is a 10-item clinician-rated measure of OCD symptom severity. Raters assess obsessions and compulsions separately in five domains: time spent, interference, distress, resistance, and control. Each domain is rated on a scale from 0 to 4. Total scores range from 0 to 40, with higher scores indicating greater symptom severity.

**Derived Variables and Statistical Analysis:** 

Sponsor: Emalex Biosciences, Inc.; Protocol No.: EBS-101-TD-301

The total score (sum of all items without imputing missing values) will be summarized by treatment group at the Baseline and Weeks 4, 8, 12, 13, 14, 15, 16, 20 and 24 visits and all questionnaire data will be displayed in a listing.

# 13. Interim Analysis

An interim analysis (IA) will be conducted after approximately 70% of Relapse events have accrued (34 Relapse events). The interim analysis will be performed by an independent statistician and governed by an independent Data Safety Monitoring Board (DSMB). The DSMB will consist of a physician experienced in the conduct of clinical studies (Chairman with TD experience), one clinician and one statistician experienced in TD will review the data at the interim analysis. The data will be cleaned by the data management group, and the analysis and reporting of the interim data to the DSMB will be the responsibility of an independent statistical group (which will not be directly involved in the conduct of the study). The DSMB will meet after the data presentation and issue recommendations. Minutes of the DSMB will be submitted to the sponsor after the study has been unblinded and will be appended to the final study report.

The 2-sided alpha level for the IA is 0.005. For the final analysis the 2-sided alpha level after IA spend will be 0.0492. If the statistical significance is reached at the IA, the DSMB can recommend stopping the study for overwhelming efficacy. However, the interim decisions for stopping for futility or potential sample size adjustments are based on the conditional power described below.

The primary efficacy endpoint is time from Randomization to Relapse defined as a loss of  $\geq$  50% of the improvement experienced on the YGTSS-TTS at the last visit in the open-label Stabilization period (Week 12), or initiation of additional medications to treat symptoms of TD, or requirement of hospitalization for worsening symptoms of TD in subjects  $\geq$  6 and < 18 years during the double-blind R/WD period for ecopipam compared to placebo. The analysis will be performed on all randomized subjects in R/WD period. The analysis method will be the same as the primary efficacy analysis as described in Section 10.1.

Assume that r is the number of Relapse events at interim analysis (r=34 in the planned interim analysis), R is the planned number of Relapse events (R=49) in this study, then the conditional power (CP) can be expressed as

CP=1-
$$\Phi(z_{int}\sqrt{\frac{r}{R-r}}+Z_{\alpha/2}\sqrt{\frac{R}{R-r}}+Z_{int}\sqrt{\frac{R-r}{r}})$$

where  $\Phi(.)$  denotes the cumulative distribution function of the standard normal distribution, and  $z_{\alpha/2}$  denotes the  $1-\alpha/2$  quantile of the standard normal distribution, and  $Z_{int}$  is z-value at interim analysis, which can be obtained from the output of PROC LIFETEST in SAS. The  $Z_{int}$  can be derived from the reported Logrank statistics and the corresponding covariance matrix

Derivation:

$$Z_{int} = \frac{O - E}{\sqrt{V}} = \frac{\sum_{j} (O_j - E_j)}{\sqrt{\sum_{j} V_j}}$$

where,

 $O_i = d_{1i}$ , Number of subjects in Ecopipam who developed Relapse, at distinct time j

This document is confidential.

SAP text Version: SAP text 3.0 6-Dec-2023

Controlled Document ID: 3903A.02, Effective Date 31-Aug-2020

$$E_j = \left(\frac{Y_{1j}}{Y_j}\right) * d_j, \qquad d_j = d_{0j} + d_{1j}, \text{ total number of Relapses at time j, } Y_{1j} = \text{Number of subjects in Ecopipam at time } j,$$

 $Y_i$  = Number of subjects at risk at time j.

$$V_j = \frac{Y_{0j}Y_{1j}d_j(Y_j-d_j)}{Y_i^2(Y_j-1)}, Y_{0j} = \text{number of subjects at risk at time j at control arm,}$$

 $d_i = d_{0j} + d_{1j}$  total number of Relapses at both control arm and Ecopipam at time j.

Based on the results of the above conditional power and the promising zone approach [8], the DSMB may make the following interim decisions:

- If p-value based on Logrank test at interim analysis is less than 0.005 and other measures (e.g., hazard ratio) imply a benefit of ecopipam over placebo, it is recommended to stop the study for overwhelming efficacy.
- 2) If 50%<CP<85%, then increase the number of required events such that CP based on the adjusted events ≥85% or reach the maximum number of Relapse events allowed, defined as two times the planned Relapse events (49 x 2 = 98).
- 3) If condition power (CP)<20%, it is recommended to stop the study for futility.
- 4) If all other cases, continue this study as planned.

No adjustment of the final alpha level will be required, other than the alpha spending of the IA, based on the CP approach.

Full details of the DSMB procedures including primary responsibilities of the DSMB, its relationship with other study components, its membership, and the purpose and timings of its meetings will be documented in a DSMB charter. These details will also include procedures to ensure confidentiality and proper communication, the guidelines to be implemented by the DSMB and an outline of the content of the closed reports (unblinded) and open reports (blinded) that will be provided to the DSMB.

